The study will be conducted following a reduced PK study design in Part A, see [Table 1](#) and [Figure 1](#). Part A will enroll participants from Group 1A (i.e., 6 healthy matched controls) and Group 2 (i.e., 6 participants with severe renal impairment and ESRD, not on dialysis). A decision to proceed to Part B will be made after the PK of pretomanid, and safety in participants enrolled in Part A have been reviewed. If Part A demonstrates at least a 50% increase in pretomanid area under the plasma concentration-time curve (AUC) in Group 2 (severe renal impairments and ESRD, not on dialysis) relative to the exposures in Group 1A (matched participants with normal renal function), then the reduced PK study will extend to the full PK study to enroll participants into Part B (i.e., to investigate mild and moderate renal impairment). All Part B groups (1B, 1C, 3, and 4) will be enrolled concurrently.

If the reduced PK study shows at least a 50% increase in AUC in patients with severe renal impairment and patients with ESRD not yet on dialysis relative to the matched healthy controls, a “full PK” renal impairment study in patients with all intermediate levels of renal function impairment should be conducted. Otherwise, no further study is recommended.

Study Population: Total 36 male and female adult participants ages of 18 to 85 years inclusive, including 18 participants with normal renal function matched against each of the renal impairment groups, and 18 renal

impaired participants (N=6 mild renal impairment, N=6 moderate renal impairment, and N=6 severe renal impairment) as defined by estimated glomerular filtration rate (eGFR) (see [Table 1](#)).

Six participants with normal renal function in each group (1A, 1B, 1C) will be matched by race, gender, age (\pm 10 years, but between 18 to 85 years of age), and body mass index (BMI) (18 to 40 kg/m²) at enrollment; eGFR \geq 90 mL/min as calculated by Modification of Diet in Renal Disease (MDRD) to each renal impairment Group 2, 3, and 4, respectively.

Group 2: Severe renal impairment: Stage 4 (eGFR 15-29 mL/min) and ESRD not on dialysis: Stage 5, MDRD (eGFR <15 mL/min).

Group 3: Mild renal impairment: Stage 2, MDRD (eGFR 60-89 mL/min).

Group 4: Moderate renal impairment: Stage 3, MDRD (eGFR 30-59 mL/min).

Number of Sites: 2

Description of Study Product or Intervention: A single oral dose of pretomanid 200 mg

Study Objectives: **Primary:**

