4.4.3 Method of Assigning Participants to Impairment Groups

There is no randomization performed for this open-label study. Participants are assigned to the 3 renal impairment groups based on their MDRD eGFR, with approximately 6 participants per renal impairment group (Groups 2, 3, and 4) and approximately 18 healthy participants will be matched to 1 or more renal impairment participants (Groups 1A, 1B, and 1C).

Enrollment will be performed through the enrollment module in the electronic data capture system, maintained by the SDCC.

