5 SAMPLE SIZE CONSIDERATIONS

A sample size of 6 per group is standard for renal impairment PK studies. Prior studies of pretomanid (PA-824) with similar dosing (200 to 250 mg) have estimated coefficients of variation (CV) of 16% to 33% for the AUC after a single dose in healthy adult participants. Assuming a 20% CV for the AUC of both groups, the probability of observing at least a 50% increase in the geometric mean ratio of AUCs given a true 100% increase is >99%. The probability of the lower bound of the 90% CI for the geometric mean ratio of AUCs being at least 1.5 in this scenario is approximately 70%.

The sample size per arm in Part B was chosen based on feasibility and appropriateness for a PK study in renal impaired participants to estimate group differences in PK parameters with adequate precision. Assuming an observed 2-fold difference between each renal impairment group and matched controls with no correlation between matched pairs and a coefficient of variation of 20%, a 90% CI for the fold difference between groups is (1.70, 2.35).

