10 PHARMACOKINETICS

PK analyses will be performed using NCA. PK concentrations and noncompartmental parameters will be summarized by renal impairment group. Statistics include the arithmetic mean, median, SD, GM, CV, min, and max. PK parameters of exposure (AUC_{last}, AUC_∞, and C_{max}) will be compared between impairment groups using ANOVA models with or without random effects. T_{max} will be compared using 90% confidence intervals calculated using the inverted rank score method. Concentrations below the quantitation limit (BQL) prior to first measurable concentration will be imputed as zero. The first BQL concentration reported in the plasma concentrations after the last measurable concentration may be imputed for the purpose of parameter estimation as the LLOQ divided by 2 only if 1) needed to estimate λ_z, 2) all other λ_z estimation criteria are met, and 3) if a visual predictive check of the imputed value appears to be consistent with the observed elimination trend. All other BQL samples will be treated as missing. Imputed concentration values will only be used for plasma parameter estimation by NCA and not included in concentration summaries, however, imputed BQL values will be indicated by imputation method in listings with methods clarified in the footnote and denoted in figures.

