T_{\max} will be summarized in each impairment group using the median, and group differences will be assessed using nonparametric confidence intervals computed using the inverted rank score method ([Table 93](#)). Medians and confidence intervals will also be computed for each site. If the confidence intervals do not overlap between sites, then the T_{\max} will also be summarized by site.

Summary box plots of PK parameters by impairment group (and site if appropriate) will also be presented ([Figure 35](#), [Figure 36](#), [Figure 37](#), [Figure 38](#), [Figure 39](#), and [Figure 40](#)).

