Site	Impairment Group	Statistic	AUC _{last} (μg*h/mL)	AUC _∞ (μg*h/mL)	C _{max} (μg/mL)
All Sites	Mild	Mean			
		90% CI of Mean			
		Fold Change ^a			
		90% CI of Fold Change			
	Moderate	Mean			
		90% CI of Mean			
		Fold Change ^a			
		90% CI of Fold Change			
	Severe	Mean			
		90% CI of Mean			
		Fold Change ^a			
		90% CI of Fold Change			
	Matched Controls	Mean			
		90% CI of Mean			
Alliance for Multispecialty Research	Mild	Mean			
		90% CI of Mean			
		Fold Change ^a			
		90% CI of Fold Change			
	Moderate	Mean			
		90% CI of Mean			
		Fold Change ^a			
		90% CI of Fold Change			
	Severe	Mean			
		90% CI of Mean			
		Fold Change ^a			
		90% CI of Fold Change			
	Matched Controls	Mean			

Table 93: Estimated Impairment Group Fold Change for Noncompartmental PK Parameters (continued)

		90% CI of Mean			
Advanced Pharma	Mild	Mean			
		90% CI of Mean			
		Fold Change ^a			
		90% CI of Fold Change			
	Moderate	Mean			
		90% CI of Mean			
		Fold Change ^a			
		90% CI of Fold Change			
	Severe	Mean			
		90% CI of Mean			
		Fold Change ^a			
		90% CI of Fold Change			
	Matched Controls	Mean			
		90% CI of Mean			

Notes: ^a Comparison is to matched controls.

Table 94: Estimated Impairment Group Shift for Noncompartmental PK Parameters

[Implementation Note: Site column will only be included if confidence intervals between sites do not overlap.]

Site	Impairment Group	Statistic	T _{max} (h)
All Sites	Mild	Median	
		90% CI of Median ^a	
		Shift ^b	
		90% CI of Shift ^a	
	Moderate	Median	
		90% CI of Median ^a	
		Shift ^b	
		90% CI of Shift ^a	
	Severe	Median	
		90% CI of Median ^a	
		Shift ^b	
		90% CI of Shift ^a	
	Matched Controls	Median	
		90% CI of Median ^a	
Alliance for Multispecialty Research	Mild	Median	
		90% CI of Median ^a	
		Shift ^b	
		90% CI of Shift ^a	
	Moderate	Median	
		90% CI of Median ^a	
		Shift ^b	
		90% CI of Shift ^a	
	Severe	Median	
		90% CI of Median ^a	
		Shift ^b	
		90% CI of Shift ^a	
	Matched Controls	Median	
		90% CI of Median ^a	
Advanced Pharma	Mild	Median	
		90% CI of Median ^a	
		Shift ^b	
		90% CI of Shift ^a	

Table 94: Estimated Impairment Group Shift for Noncompartmental PK Parameters (continued)

	Moderate	Median	
		90% CI of Median ^a	
		Shift ^b	
		90% CI of Shift ^a	
	Severe	Median	
		90% CI of Median ^a	
		Shift ^b	
		90% CI of Shift ^a	
	Matched Controls	Median	
		90% CI of Median ^a	

Notes:
^aConfidence limits will be estimated using the inverted rank score method.
^bComparison is to matched controls.

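### The by-site 90% confidence intervals for median Tmax cannot reach 90% in groups of six split over two sites

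*SAP*

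**What the plan says.** SAP section 10 fixes the level and the method: Tmax "will be compared using 90% confidence intervals calculated using the inverted rank score method". Section 10.2.3 adds the site layer, "Medians and confidence intervals will also be computed for each site", and then a rule that begins "If the confidence intervals do not overlap between sites, then the" and ends in a by-site Tmax summary.

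The output is the Table 94 shell (10.2.3 cites Table 93, but the Tmax shell is numbered 94). It has a row labelled "90% CI of Median", and a row for the 90% CI of the shift against controls, for each impairment group within each of two named sites. Controls form one pooled row per site, with a median interval only. An implementation note says: "Site column will only be included if confidence intervals between sites do not overlap".

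The sizes come from elsewhere. The Protocol Summary gives "Number of Sites: 2". SAP section 5 says "A sample size of 6 per group is standard for renal impairment PK studies". SAP 4.4.3 plans that "approximately 18 healthy participants will be matched to 1 or more renal impairment participants"; if Part B does not run, there are six controls. Neither document states a site split, a minimum cell size, an attained-coverage statement or a fallback.

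**The concern.** A nonparametric interval for a median takes its limits from the observed values, so its best possible coverage depends only on how many values there are. Six participants divided between two sites leave very few in each cell. If 90% is out of reach there, the report would print a confidence level that the design cannot deliver, for a parameter listed under the primary plasma PK outcome (SAP 3.2.1.1). The same intervals also decide whether Tmax is shown by site, so the behaviour of that screen would depend on an unplanned enrolment split.

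**Working it through.** **Inputs.** Level 90% and rank-based method (SAP 10); two sites (Protocol Summary); six per renal group (SAP 5); six controls after Part A only, about 18 after both parts (SAP 4.4.3). The site split is not given, so I take every split of six: 3/3, 4/2, 5/1 and 6/0.

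**Figure to reproduce.** The plan gives no coverage calculation for Tmax. The only stated figure is the nominal 90%, so the check is whether each cell can attain it.

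**Median interval.** The widest finite distribution-free interval runs from the smallest to the largest value. It misses the median only when all n values fall on the same side, so its guaranteed coverage for a continuous variable is 1 − 2(1/2)^n. Inverting the sign test or the signed-rank test has the same ceiling.

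- n = 1: 1 − 2(0.5) = 0%
- n = 2: 1 − 2(0.25) = 50%
- n = 3: 1 − 2(0.125) = 75%
- n = 4: 1 − 2(0.0625) = 87.5%
- n = 5: 1 − 2(0.03125) = 93.75%
- n = 6: 1 − 2(0.015625) = 96.9%

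Ninety per cent therefore needs five in the cell, and 5 + 5 = 10 in a group for both sites to reach it. For a group of six:

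| Split | Larger site | Smaller site |
|---|---|---|
| 3/3 | 75% | 75% |
| 4/2 | 87.5% | 50% |
| 5/1 | 93.75% | 0% |
| 6/0 | 96.9% | no second site |

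Every split that uses both sites has at least one cell below 90%. With all six together, 90% is attainable: 96.9% from the extremes, or 90.6% from a narrower signed-rank interval.

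**Pooled controls.** With 18 controls split 9/9, the second-smallest to second-largest values give 96.1%. Any split with at least five at the smaller site reaches 90%.

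**Shift interval.** For m renal and n control participants at a site, the ceiling is 1 − 2/C(m+n, m).

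- 3 v 3: 1 − 2/20 = 90%
- 3 v 9: 1 − 2/220 = 99.1%
- 2 v 9: 1 − 2/55 = 96.4%
- 2 v 2: 1 − 2/6 = 66.7%
- 1 v 9: 1 − 2/10 = 80%

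**Overlap trigger.** Assume the software returns the minimum and maximum, there is no true site difference, and there are no ties. Two ranges fail to overlap only if all the values at one site lie below all those at the other. The probability is 2/C(6, k), with k at the smaller site.

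- 3:3: 2/20 = 10%
- 4:2: 2/15 = 13.3%
- 5:1: 2/6 = 33.3% (a single value is treated as an interval)

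For comparison, two genuine large-sample 90% intervals of equal precision fail to overlap when the standardised difference exceeds 1.645 × √2 = 2.326, which happens about 2% of the time.

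If groups are independent and all split 3:3, the chance of at least one false trigger is 1 − 0.9² = 19% in Part A (severe group and six controls). For the three renal groups after both parts, leaving pooled controls aside, it is 1 − 0.9³ = 27%.

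**The case against.** A reader might infer more than the plan supports, in five ways.

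*No interval in the site blocks can be a 90% interval.* The documents do not bear this out. The shift intervals and the pooled-control medians can reach 90% at the cell sizes shown above. The limit is on the median interval in small cells.

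*The overlap check is invalid.* It is better called miscalibrated. At 3:3 its 10% false-trigger rate equals the p < 0.10 level of the site-interaction screen for AUC and Cmax in SAP 10.2.3. It becomes looser as the split becomes more uneven. The percentages rest on an assumption about software: SAP section 14 names WinNonlin, SAS and R but no procedure for this interval. If the limits came back missing or unbounded, the rule would be undefined or would never fire.

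*A mislabelled interval will certainly be printed.* The Table 94 note makes the site rows conditional on non-overlap. On the null figures above they would stay out in 90%, 87% or 67% of groups.

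*The ceiling applies under any reading.* The sentence in 10.2.3 says for each site, not for each group within site. Pooled over groups, the smaller site could hold up to 6 of 12 (Part A) or 18 of 36 (both parts), and 90% would be attainable. The shell, however, lays out group-by-site cells, so the pooled reading conflicts with the planned output.

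*Main conclusions are at risk.* They are not. The Part B decision uses AUC (Protocol 10.1), and the all-sites Tmax rows remain whether or not the trigger fires.

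Ties deserve separate mention. The ceiling is the guaranteed level for a continuous variable, and tied values can raise actual coverage. With assumed Tmax values of 2, 4, 5, 6 and 8 hours and probabilities 0.10, 0.25, 0.30, 0.25 and 0.10, three observations cover the median of 5 with probability 1 − 2(0.35)³ = 91%. This cannot be relied on, and SAP 10.2.2.1 uses actual sampling times, which makes exact ties less likely.

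These points limit the scope and the consequence. The mismatch between the label and the attainable coverage remains.

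**Conclusion.** The concern holds in a narrow form. In each renal group of six enrolled at both sites, and in the controls if only Part A runs, at least one site cell carries a 90% label for the median Tmax interval that it cannot meet. Guaranteed coverage at the smaller site is at most 75%. Showing severe impairment and ESRD in separate columns, as SAP section 17 directs, would make some cells smaller still.

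The coverage result assumes a continuous Tmax and the group-by-site layout of the shell. The trigger rates of 10%, 13% and 33% also assume minimum and maximum limits, no ties and no site difference. This is a labelling and screening defect in a secondary display of a listed parameter. It is worth correcting but does not affect the trial's main conclusions.

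**What to change.** In SAP 10.2.3 and the Table 94 shell:

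- Drop the site-level 90% CI of the median in any cell with fewer than five participants.
- Drop the overlap trigger.
- Report the site-level median Tmax with minimum and maximum, labelled as a range.
- Keep the all-sites median and shift with their 90% CIs.
- Keep site-level shift or control intervals only where the cell sizes make 90% attainable, and say that they are within impairment group.
- Correct the table number cited in 10.2.3.

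The cost is a few lines of SAP text and a shell edit before database lock, with no change to data collection. The loss is that small cells will have no formal site-level interval for median Tmax.

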11 IMMUNOGENICITY

Not applicable.

12 OTHER ANALYSES

Not applicable.

13 REPORTING CONVENTIONS

P-values ≥ 0.001 and ≤ 0.999 will be reported to 3 decimal places; p-values less than 0.001 will be reported as “ <0.001 ”. The mean, standard deviation, and other statistics will be reported to 1 decimal place greater than the original data. The minimum and maximum will use the same number of decimal places as the original data. Proportions will be presented as 2 decimal places; values greater than zero but <0.01 will be presented as “ <0.01 ”. Percentages will be reported to the one decimal place; values greater than zero but $< 1\%$ will be presented as “ $<1\%$ ”; values greater than 99% but less than 100% will be reported as $>99\%$. 100% will be reported as 100%. Estimated parameters, not on the same scale as raw observations (e.g. regression coefficients) will be reported to 3 significant figures. Drug concentrations, AUCs, and C_{max} and their summary statistics will have the same number of significant digits as the drug concentrations reported by the bioanalytical laboratory. Other PK parameters will be reported to 1 decimal place.

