Overall, oral CL/F values (~8 L/hr) for pretomanid at a 200 mg dose are considerably less than the hepatic blood flow for a 70 kg human (1450 mL/min, 87.0 L/hr), suggesting that pretomanid is not highly extracted by the liver. Furthermore, the apparent V_d/F after a 200 mg dose was approximately

175 L, which is considerably higher than the total volume of body water (~42 L), indicating that pretomanid is distributed out of plasma.

Pretomanid binding to human plasma protein is 86.4%, with the majority of the binding to human serum albumin [18]. In the presence of rifampicin (strong cytochrome [CYP] 3A4 inducer) and efavirenz (moderate CYP3A4 inducer), pretomanid average concentration over a dosing interval (C_{avg}) is reduced by 66% and 35%, respectively. Therefore, strong and moderate CYP3A4 inducers should be avoided with pretomanid.

Once-daily oral administration of pretomanid 400 mg for 14 days did not appear to significantly inhibit CYP3A4 in healthy participants, based on the results of a drug-drug interaction study with midazolam, a sensitive probe substrate for drugs metabolized by CYP3A enzymes. Results of in vitro investigations using human liver microsomes also support a low risk of drug-drug interactions with pretomanid. In 2 mass-balance studies in healthy participants [18], approximately 91% of the administered radioactive dose was recovered in the urine (65% and 53%) and feces (26% and 38%). The majority of urinary and fecal radioactivity elimination occurred within 6 to 7 days after dosing. Comparisons of plasma and whole blood total radioactivity PK parameters to plasma pretomanid PK parameters suggest that the majority of the administered dose is converted to pretomanid metabolites, after which time total radioactivity in blood is eliminated slowly from the body.

No clinically significant differences in the PK of pretomanid were observed based on sex, body weight, race, pulmonary TB status, or HIV status.

The effect of renal or hepatic impairment on the PK of pretomanid is unknown.

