Patients with renal impairment, particularly severe renal impairment or end stage renal disease (ESRD), may have an increased risk of drug exposure and may require lower doses of certain drugs compared to patients with normal renal function [37]. According to FDA and Europe, the Middle East, and Africa (EMEA) guidelines, a pharmacokinetic (PK) study should be carried out during the development phase of a new drug that is likely to be used in patients with renal dysfunction and whose pharmacokinetics are likely to be significantly altered in renally impaired patients [38, 39]. Less than 1% of unmetabolized pretomanid is excreted in the urine. [18]. Therefore, like other commonly used anti-TB drugs such as ethambutol and pyrazinamide, which are at least partly eliminated through kidneys, the PK of pretomanid must be studied in patients with CKD. CKD is a very common clinical disease with estimated prevalence of 8 to 16%, and CKD patients globally, particularly those in advanced stages, have significantly increased risk of developing TB [11-13].

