3.2.1.2 Urine PK of Pretomanid

The urine PK of a single dose of pretomanid will be assessed from urine collected up to 1 hour pre-dose, 0-4, 4-8, 8-12, 12-24, 24-48, 48-72, and 72-96 hours post-dose. The following PK parameters will be determined using urine volumes and concentrations:

$Ae(0-t)$: Cumulative amount excreted into the urine from time 0 to the time t

$Ae\%$ Dose: Fraction of dose excreted into the urine

CLR : Renal clearance

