$$\frac{V_z}{F} = \frac{Dose}{\lambda_z \times AUC_{\infty}} = \frac{CL}{\lambda_z \times F}$$

$Ae_{(0-t)}$ is defined as the total amount of drug excreted unchanged, or amount of metabolite, in urine over the time interval 0 to time t. It is calculated as the sum of all the concentrations measured in the urine samples pooled over each interval multiplied the total respective volume of each urine sample.

%AeDose is represent the percent of the dose that was excreted unchanged in urine. It is calculated as the shown below:

$$\%AeDose = \frac{Ae_{(0-t)}}{Dose}$$

The renal clearance (CL_R) is defined as the clearance attributable to the renal route. Its calculation requires both urine and non-urine (typically plasma) data to be collected from the same route and regimen in the same individuals. It can then be estimated as the amount excreted in urine divided by the observed AUC in the non-urine matrix over the equivalent time interval as the urine data was collected, as shown below:

$$CL_R = \frac{Ae_{(0-t)}}{AUC_{(0-t)}}$$

Where $Ae_{(0-t)}$ is the amount excreted in urine and $AUC_{(0-t)}$ is the AUC in the non-urine matrix.

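### The SAP's one-decimal rule and a missing factor of 100 leave λz, renal clearance and percent of dose in urine largely unreadable for pretomanid

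*SAP*

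**What the plan says.** SAP section 13 sets display precision. Concentrations, AUC and Cmax, with their summaries, "will have the same number of significant digits as the drug concentrations reported by the bioanalytical laboratory". The next sentence covers everything else: "Other PK parameters will be reported to 1 decimal place". SAP 6.1 promises more detail on PK reporting in section 10, but section 10 sets no number of decimals, so nothing there overrides this.

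The same paragraph of section 13 has three other rules that could be read as applying:

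- For proportions: "Proportions will be presented as 2 decimal places; values greater than zero but" under 0.01 appear as `<0.01`.
- For percentages: "Percentages will be reported to the one decimal place", and values above zero but under 1% appear as `<1%`.
- Estimated parameters on a different scale from the raw data, with regression coefficients as the example, get three significant figures.

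Means and medians also gain one decimal over the raw values (SAP 6.1 and 13). The SAP does not say which rule prevails for λz or Ae%Dose.

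On the urine parameter, SAP 3.3.1 says in words that "AeDose is represent the percent of the dose that was excreted unchanged in urine", but the formula under it is Ae(0-t) divided by Dose, with no factor of 100. The %AUCex formula in the same section does have that factor. SAP 3.2.1.2 and 4.5.1 label the quantity "Fraction of dose excreted into the urine".

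**The concern.** λz is a listed primary plasma parameter (SAP 3.2.1.1). Ae%Dose and CLR are listed primary urine parameters (SAP 3.2.1.2), and CLR is the one that directly measures renal handling. If their expected values lie below the last printed digit, the displays cannot do much to separate impaired participants from controls.

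For CLR and Ae%Dose no other planned display helps. The model-based comparison covers only AUClast, AUC∞ and Cmax, and the box plots cover Cmax, Tmax, AUC∞, AUClast, CL/F and Vd/F. The two urine parameters appear only in shell Tables 89 to 92 and Listing 24.

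The formula is a separate defect. A quantity labelled as a percent and calculated as a fraction is misread by a factor of 100, whatever the rounding.

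**Working it through.** The documents print no expected λz, CLR or Ae%Dose, so there is no stated figure to reproduce. The check derives each from background values and applies the rounding.

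**Inputs**

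- Half-life about 18 h (Protocol 2.1.5.2).
- Clearance: "Overall, oral CL/F values (~8 L/hr) for pretomanid at a 200 mg dose" (Protocol 2.1.5.2). Vd/F about 175 L (same section).
- Urinary excretion: "Less than 1% of unmetabolized pretomanid is excreted in the urine" (SAP 2), read here as under 1% of the dose excreted unchanged, so fe < 0.01.
- Dose 200 mg (SAP 4.4.1). Ae is in µg and CLR in L/h (shell Table 89).

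**λz = ln 2 / t½**

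- ln 2 / 18 = 0.0385 per h, printed 0.0.
- Cross-check from (CL/F)/(Vd/F): 8/175 = 0.0457 per h (half-life 15.2 h), printed 0.0.
- If clearance fell by a third: 0.0385/1.5 = 0.0257 per h (half-life 27 h), printed 0.0.
- The printed value reaches 0.1 only at λz of 0.05 or more, that is t½ of ln 2/0.05 = 13.9 h or less. Assume a log-normal half-life with CV 20% to 33% (the documents give CVs in this region for AUC, not half-life). Then 9% to 21% of participants would print 0.1 at a geometric mean of 18 h, and 33% to 39% at 15.2 h.

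**CLR = Ae/AUC = fe × CL/F**

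The documents give only the upper bound on fe, so the rows below 1% are assumed values.

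| fe | CLR at CL/F 8 L/h | Printed |
|---|---|---|
| 1% (ceiling) | 0.080 | 0.1 |
| 0.75% | 0.060 | 0.1 |
| 0.5% | 0.040 | 0.0 |
| 0.25% | 0.020 | 0.0 |
| 0.1% | 0.008 | 0.0 |

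The switch from 0.1 to 0.0 is at fe = 0.05/8 = 0.625%. If CL/F is instead taken from the steady-state AUC of 38 to 40 µg·hr/mL in Protocol 2.1.5.2, it is 200/40 = 5.0 to 200/38 = 5.3 L/h. The ceiling is then 0.050 to 0.053 L/h, and practically every value prints 0.0.

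**%AeDose**

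- As written, Ae/Dose is below 0.01. It prints 0.0 under the PK-parameter rule, `<0.01` under the proportion rule and `<1%` under the percentage rule.
- With the factor of 100 added, fe of 0.0025, 0.005 and 0.0075 become 0.25%, 0.5% and 0.75%, but the percentage rule still prints all three as `<1%`. The factor alone does not restore the information.

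**What one decimal does not damage**

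- t½ (18.0 h), CL/F (8.0 L/h) and Vd/F (about 175 L).
- Ae, which can be as large as 0.01 × 200,000 µg = 2,000 µg.

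**The case against.** A reader might infer that all three parameters will certainly print as 0.0 and that the report therefore cannot show a renal effect. The documents do not support that.

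- Ae%Dose may fall under the `<0.01` or `<1%` rule, so a printed zero is not settled.
- SAP 3.3.1 estimates λz by linear regression, so the three-significant-figure rule could be claimed for it.
- Means and medians may carry a second decimal: mean λz could show 0.04 against 0.03, and mean CLR 0.08 against 0.04. An individual CLR can also cross from 0.1 to 0.0.
- The information survives elsewhere. Half-life is ln 2/λz. Everyone receives the same dose, so Ae%Dose is Ae over a constant, and Ae in µg sits in the same table. CLR can be approximated from Ae and AUC.
- Rounding affects display, not calculation. The fold-change model uses log AUClast, AUC∞ and Cmax, and the Part B criterion is AUC.

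All of this stands, and it limits the point. It does not remove it. The less-than displays tell the reader no more than 0.0 does, because the whole expected range lies under 1%. A second decimal on a mean still leaves one significant figure: λz shown as 0.04 covers half-lives from ln 2/0.045 = 15.4 h to ln 2/0.035 = 19.8 h. Several candidate rules with no order of precedence are themselves a gap. A reader should not have to rebuild a listed primary parameter from neighbouring columns. The contradiction between percent, fraction and formula is untouched by any of these arguments.

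**Conclusion.** The point holds as a precision and definition error in listed primary parameters. Under the one-decimal rule, a typical individual λz prints as 0.0 and CLR as 0.0 or 0.1. %AeDose is 100-fold too low under its own label, and each rule that might govern it gives an uninformative display. Differences between groups in CLR and Ae%Dose are largely obscured in the only outputs that show them.

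This rests on the background values in the documents (half-life about 18 h, CL/F about 8 L/h, under 1% unchanged in urine) applying roughly to this study, and it concerns the parent drug. No CLR is given anywhere; only its ceiling follows from the documents. The conclusion does not extend to the exposure comparison, to the Part B decision, or to CL/F, Vd/F, Ae or half-life.

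**What to change.** - SAP 13: report λz, CLR and Ae%Dose, with their summary statistics, to three significant figures, and state that Ae%Dose is exempt from the `<0.01` and `<1%` rules. At that precision λz would read 0.0385 against 0.0257 for half-lives of 18 h and 27 h, and CLR 0.0800 against 0.0400 L/h for fe of 1% and 0.5% at CL/F 8 L/h.
- SAP 3.3.1: write %AeDose = 100 × Ae(0-t)/Dose, with both in the same mass unit. The shell has Ae in µg and the dose is in mg.
- SAP 3.2.1.2 and 4.5.1: change the label from fraction to percentage.

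No change is needed for CL/F, Vd/F or Ae, which are adequately shown at one decimal. The cost is SAP wording and the display format of a few columns, with no new data or analysis.
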